## Local Number of Subjects

*Indicate the total number of subjects that will be enrolled or records that will be reviewed locally.*

Response:

We plan to enroll 100 participants in each aim for a total of 200.

*If applicable, indicate how many subjects you expect to screen to reach your target sample (i.e. your screen failure rate).*

Response:

Individuals will complete screening questions online. We are unsure of the number of people who may click on the study's website without being a member of the target population.

*Justify the feasibility of recruiting the proposed number of eligible subjects within the anticipated recruitment period. For example, how many potential subjects do you have access to? What percentage of those potential subjects do you need to recruit?*

Response:

According to the NASW-NYS website (the New York State chapter of the National Association of Social Workers, there are 115,000 practicing social workers in the state. We plan to utilize a multi-pronged recruitment strategy using regional listservs, NASW-NYS newsletter ads, and social media to reach as many of these individuals as possible.

We are unsure at this stage of how many individuals may be exposed to advertising mechanisms, but we feel that recruiting 200 over multiple months should be reasonable.

## Inclusion and Exclusion Criteria\*

*Describe the criteria that define who will be **included** in your final study sample.*

*NOTE: This may be done in bullet point fashion.*

Response:

- Social work degree (BSW, MSW, DSW, or PhD in Social Work or Social Welfare
- Current employed at least part-time in social work practice.
- Fluent in English
- Aged 18 or older.

*Describe the criteria that define who will be **excluded** from your final study sample.*

*NOTE: This may be done in bullet point fashion.*

Response:

Anyone who does not meet all four criteria listed above. Anyone who participated in Aim 1 will be excluded from Aim 2.

*Indicate specifically whether you will include any of the following special populations in your study using the checkboxes below.*

*NOTE: Members of special populations may not be targeted for enrollment in your study unless you indicate this in your inclusion criteria.*

Response:

- Adults unable to consent
- Individuals who are not yet adults (infants, children, teenagers)
- Pregnant women
- Prisoners

*Indicate whether you will include non-English speaking individuals in your study.*

*Provide justification if you will exclude non-English speaking individuals.*

*In order to meet one of the primary ethical principles of equitable selection of subjects, non-English speaking individuals may **not** be routinely excluded from research as a matter of convenience.*

*In cases where the research is of therapeutic intent or is designed to investigate areas that would necessarily require certain populations who may not speak*

*English, the researcher is required to make efforts to recruit and include non-English speaking individuals. However, there are studies in which it would be reasonable to limit subjects to those who speak English. Some examples include pilot studies, small unfunded studies with validated instruments not available in other languages, studies with numerous questionnaires, and some non-therapeutic studies which offer no direct benefit.*

Response:

The SAFR intervention is currently available only in English. Translation is not possible at this time.

## **Vulnerable Populations\***

*If the research involves special populations that are considered vulnerable, describe the safeguards included to protect their rights and welfare.*

*NOTE: You should refer to the appropriate checklists, referenced below, to ensure you have provided adequate detail regarding safeguards and protections. You do not, however, need to provide these checklists to the IRB.*

*For research that involves **pregnant women**, safeguards include:*

*NOTE CHECKLIST: Pregnant Women (HRP-412)*

Response:

Although we are not intentionally recruiting pregnant individuals, some individuals who participate in this study may be pregnant. No aspect of this project presents additional risk above and beyond what the pregnant individual would normally encounter at work.

**N/A:** This research does not involve pregnant women.

*For research that involves **neonates of uncertain viability or non-viable neonates**, safeguards include:*

*NOTE CHECKLISTS: Non-Viable Neonates (HRP-413), or Neonates of Uncertain Viability (HRP-414)*

Response:

**N/A:** This research does not involve non-viable neonates or neonates of uncertain viability.

*For research that involves **prisoners**, safeguards include:*

*NOTE CHECKLIST: Prisoners (HRP-415)*

Response:

**N/A:** This research does not involve prisoners.

*For research that involves **persons who have not attained the legal age for consent to treatments or procedures involved in the research (“children”)**, safeguards include:*

*NOTE CHECKLIST: Children (HRP-416)*

Response:

**N/A:** This research does not involve persons who have not attained the legal age for consent to treatments or procedures (“children”).

*For research that involves **cognitively impaired adults**, safeguards include:*

*NOTE CHECKLIST: Cognitively Impaired Adults (HRP-417)*

Response:

**N/A:** This research does not involve cognitively impaired adults.

*Consider if other specifically targeted populations such as students, employees of a specific firm, or educationally or economically disadvantaged persons are vulnerable. Provide information regarding their safeguards and protections, including safeguards to eliminate coercion or undue influence.*

Response:

N/A

## Eligibility Screening\*

*Describe screening procedures for determining subjects' eligibility. Screening refers to determining if prospective participants meet inclusion and exclusion criteria.*

 *Include all relevant screening documents with your submission (e.g. screening protocol, script, questionnaire).*

Response:

Individuals will be directed to a link on REDCap to determine eligibility. We have attached the screening questions that will be posted on the website.

“Study Eligibility Determination” attached

**N/A:** There is no screening as part of this protocol.

## Recruitment Methods

**N/A:** This is a records review only, and subjects will not be recruited.

*NOTE: If you select this option, please make sure that all records review procedures and inclusion/exclusion screening are adequately described in other sections.*

*Describe when, where, and how potential subjects will be recruited.*

*NOTE: Recruitment refers to how you are identifying potential participants and introducing them to the study. Include specific methods you will use (e.g. searching charts for specific ICD code numbers, Research Participant Groups, posted advertisements, etc.).*

Response:

We are working with Fahlgren Mortine to develop a social media campaign to recruit study participants. In addition to social media, we will utilize regional UB listservs (UB SSW Alumni, Field Education), word of mouth, and advertisements in the National Association of Social Workers NYS newsletter to recruit participants.

There will be two waves of recruitment, one for each Aim of the study, and recruitment methods will be the same. In all cases, individuals will be provided a link to click on that directs them to a landing page (hosted by the SSW) that provides information about the current Aim with instructions on how to enroll.

*Describe how you will protect the privacy interests of prospective subjects during the recruitment process.*

*NOTE: Privacy refers to an individual's right to control access to him or herself.*

Response:

Aside from demographic information, the only identifying information we will have for participants is their email addresses – necessary for the repeated contact required in both Aims of the study. These email addresses will never be publicly revealed.

*Identify any materials that will be used to recruit subjects.*

*NOTE: Examples include scripts for telephone calls, in person announcements / presentations, email invitations.*

□ *For advertisements, include the final copy of printed advertisements with your submission. When advertisements are taped for broadcast, attach the final audio/video tape. NOTE: You may submit the wording of the advertisement prior to taping to ensure there will be no IRB-required revisions, provided the IRB also reviews and approves the final version.*

Response:

We have attached recruitment materials developed in consultation with Fahlgren Mortine and our graphic designer.

## Procedures Involved\*

*Provide a description of **all research procedures or activities** being performed and when they are performed once a subject is screened and determined to be eligible.  
Provide as much detail as possible.*

*NOTE: This should serve as a blueprint for your study and include enough detail so that another investigator could pick up your protocol and replicate the research. For studies that have multiple or complex visits or procedures, consider the addition of a schedule of events table in in your response.*

Response:

Aim 1:

Participants will be recruited as described above. All advertising materials will include a link to a website (hosted by the UB School of Social Work) that describes study aims. If

they click the button to continue, they will be taken to REDCap and screened for eligibility. After passing those criteria, they will be directed to the informed consent form. We will obtain their emails at this stage and send them a copy of the informed consent document.

For those who agree to participate, they will be taken to the initial survey, also hosted by REDCap. We expect this survey will take about 20-30 minutes to complete.

After one month, an invitation to complete a similar survey (minus demographic questions) will be sent to the email address they provided. A follow-up email will be sent to anyone who does complete the second survey within one month.

Participants will be emailed a prepaid US Bank gift card after completing each survey, using the Study Card Program Group under The University at Buffalo Office of Financial Management, in conjunction with U.S. Bank.

At the conclusion of the study, participants in Aim 1 will be given access to the SAFR intervention course at no cost.

#### Aim 2:

The initial steps of this Aim will be the same as Aim 1 above: same recruitment and screening process (but with a new sample of 100 participants), with the addition of a question to determine whether they participated in Aim 1. The informed consent document will describe this study's procedures. The next link will provide the pre-test assessment, including their email address for later contact. Following block randomization within REDCap, they will find out which arm of the study they were assigned to:

**Intervention group:** The intervention group will be granted access to the online course, which takes approximately 6 hours to complete. Because the SAFR intervention is online and self-paced, they will be given four weeks to complete the course, with reminders coming once a week to encourage completion.

One month after completing the pre-test, they will be emailed a link to complete the post-test, with a reminder sent out after one week to anyone who has not completed the survey. This assessment will also include questions about the course, including open-ended questions about what worked and didn't work.

Three months after completing the pre-test, they will be emailed a link to complete the follow-up assessment, with a reminder sent out after one week to anyone who has not completed the survey.

**Control group:** The control group will receive the pre-, post-, and follow-up assessments on the same timeline as the intervention group, although they will not be asked to give feedback on the SAFR intervention. At the conclusion of the study, they will be invited to receive the intervention at no cost.

All participants will receive UB Bank cash gift cards for completing all surveys, as described below.

*Describe what data will be collected.*

*NOTE: For studies with multiple data collection points or long-term follow up, consider the addition of a schedule or table in your response.*

Response:

Aim 1:

Survey responses to the first and second survey will be collected using REDCap.

Aim 2:

Survey answers to all three assessments will be collected using REDCap. In addition, the UB SSW Continuing Education Website, which will host the SAFR intervention, retains data on how many people did not complete the course, how well they did on internal quizzes, and their time to completion.

*☐ List any instruments or measurement tools used to collect data (e.g. questionnaire, interview guide, validated instrument, data collection form).*

*Include copies of these documents with your submission.*

Response:

The following instruments will be included:

Screening tool (same for both aims of the study)

Aim 1:

Phase 1 First survey

Phase 2 Second survey

Aim 2:

Phase 2 Pretest [same for both intervention and control groups]

Phase 2 Posttest

Phase 2 Additional Questions for Intervention group Posttest [questions will be delivered through UB School of Social Work Continuing Education Course Interface]

Phase 2 Follow-up [same for both intervention and control groups]

*Describe any source records that will be used to collect data about subjects (e.g. school records, electronic medical records).*

Response:

N/A

*Indicate whether or not **individual** subject results, such as results of investigational diagnostic tests, genetic tests, or incidental findings will be shared with subjects or*

*others (e.g., the subject's primary care physician) and if so, describe how these will be shared.*

Response:

N/A

*Indicate whether or not study results will be shared with subjects or others, and if so, describe how these will be shared.*

Response:

N/A

## Study Timelines\*

*Describe the anticipated duration needed to enroll all study subjects.*

Response:

### Timeline for study activities (2023):

	Jan	Feb	Mar	Apr	May	Jun	Jul	Aug	Sep	Oct	Nov	Dec
Survey 1 for Aim 1		X	X									
Survey 2 for Aim 1			X	X								
Analyze data on measures; implement needed changes.				X	X							
Recruit for Aim 2; pre-test and course begins						X	X	X				
Post-test for both arms.							X	X	X			
Follow-up survey.									X	X	X	
Analyze data.										X	X	

*Describe the duration of an individual subject's participation in the study. Include length of study visits, and overall study follow-up time.*

Response:

Aim 1:

One survey that takes approximately 30 minutes to complete.

A similar follow-up survey one month later.

Aim 2: Intervention group:

Three surveys spread across three months.

Pre-test should take about 20-30 minutes

SAFR intervention takes about 6 hours  
Post-test one month later takes about 20-30 minutes  
Follow-up two months later takes about 15-20 minutes.

Aim 2: Control group:  
Three surveys spread across three months.  
Pre-test should take about 20-30 minutes  
Post-test one month later takes about 15-20 minutes  
Follow-up two months later takes about 15-20 minutes.

*Describe the estimated duration for the investigators to complete this study (i.e. all data is collected and all analyses have been completed).*

Response:  
One year (see timeline above).

## Setting

*Describe all facilities/sites where you will be conducting research procedures. Include a description of the security and privacy of the facilities (e.g. locked facility, limited access, privacy barriers). Facility, department, and type of room are relevant. Do not abbreviate facility names.*

*NOTE: Examples of acceptable response may be: "A classroom setting in the Department of Psychology equipped with a computer with relevant survey administration software," "The angiogram suite at Buffalo General Medical Center, a fully accredited tertiary care institution within New York State with badge access," or, "Community Center meeting hall."*

Response:  
All activities will be conducted online.

*For research conducted outside of UB and its affiliates, describe:*

- *Site-specific regulations or customs affecting the research*
- *Local scientific and ethical review structure*

*NOTE: This question is referring to UB affiliated research taking place outside UB, i.e. research conducted in the community, school-based research, international research, etc. It is not referring to multi-site research. UB affiliated institutions include Kaleida Health, ECMC, and Roswell Park Cancer Institute.*

Response:

**N/A:** This study is not conducted outside of UB or its affiliates.

## Community-Based Participatory Research

*Describe involvement of the community in the design and conduct of the research.*

*NOTE: Community-Based Participatory Research (CBPR) is a collaborative approach to research that equitably involves all partners in the research process and recognizes the unique strengths that each brings. CBPR begins with a research topic of importance to the community, has the aim of combining knowledge with action and achieving social change to improve health outcomes and eliminate health disparities.*

Response:

**N/A:** This study does not utilize CBPR.

*Describe the composition and involvement of a community advisory board.*

Response:

**N/A:** This study does not have a community advisory board.

***Describe other resources available to conduct the research.***

*Describe the time and effort that the Principal Investigator and research staff will devote to conducting and completing the research.*

*NOTE: Examples include the percentage of Full Time Equivalents (FTE), hours per week. The question will elicit whether there are appropriate resources to conduct the research.*

Response:

Drs. [name] and [name] will devote 10% of their time to this study throughout the study.

[name] will devote 2% of this time to this study.

[name] will devote 10 hours per week, of 50% FTE for a student, to this study.

*Describe the availability of medical or psychological resources that subjects might need as a result of anticipated consequences of the human research, if applicable.*

*NOTE: One example includes: on-call availability of a counselor or psychologist for a study that screens subjects for depression.*

Response:

We do not anticipate that participants will experience distress as a result of participating in this study. However, they will be given information about 988 crisis services accessible from anywhere in New York during the consent process.

*Describe your process to ensure that all persons assisting with the research are adequately informed about the protocol, the research procedures, and their duties and functions.*

Response:

## Other Approvals

*Describe any approvals that will be obtained prior to commencing the research (e.g., school, external site, funding agency, laboratory, radiation safety, or biosafety).*

Response:

**N/A:** This study does not require any other approvals.

## Provisions to Protect the Privacy Interests of Subjects

*Describe how you will protect subjects' privacy interests during the course of this research.*

*NOTE: Privacy refers to an individual's right to control access to him or herself. Privacy applies to the person. Confidentiality refers to how data collected about individuals for the research will be protected by the researcher from release. Confidentiality applies to the data.*

*Examples of appropriate responses include: "participant only meets with a study coordinator in a classroom setting where no one can overhear", or "the participant is reminded that they are free to refuse to answer any questions that they do not feel comfortable answering."*

Response:

Participants will have no direct contact with the research team or anyone else in the study.

*Indicate how the research team is permitted to access any sources of information about the subjects.*

*NOTE: Examples of appropriate responses include: school permission for review of records, consent of the subject, HIPAA waiver. This question **does apply** to records reviews.*

Response:

We will not have access to any data beyond what the participants supply through survey tools.

## **Data Management and Analysis\***

*Describe the data analysis plan, including any statistical procedures. This section applies to both quantitative and qualitative analysis.*

Response:

Aim 1:

Items in all scales will be analyzed for variance and proper range. Scales will be examined for internal reliability, test-re-test reliability, content validity, and factorial reliability as appropriate. Any items or scales that demonstrate problematic results will be revised as needed before use in Aim 2.

Aim 2:

Scores on all scales will be compared over time (pre-, post-, and follow-up tests) and across groups (intervention/control groups) using either mixed linear models or generalized estimating equations as appropriate. Analyses will be performed with a focus on estimation of parameters for use in the planning of a subsequent comparative trial designed to fully assess intervention efficacy with a national sample. Supportive analyses that adjust for participant covariates will also be considered.

SPSS and SAS will be used for all analyses.

*If applicable, provide a power analysis.*

*NOTE: This may not apply to certain types of studies, including chart/records reviews, survey studies, or observational studies. This question is asked to elicit whether the investigator has an adequate sample size to achieve the study objectives and justify a conclusion.*

Response:

Not applicable at this time as the effect sizes from this intervention are unknown.

*Describe any procedures that will be used for quality control of collected data.*

Response:

We will check for proper importation from REDCap into downloaded datasets. We will also check that respondent answers are appropriately recorded per scale expectations.

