## Objectives\*

*Describe the purpose, specific aims, or objectives of this research.*

Response:

Specific Aim 1: To test measurement tools that can be used to assess the efficacy of SAFR on theorized outcomes. Measures that have been used to assess similar

interventions for other professionals, notably medical doctors, will be modified for use with our population. The measures assess clinicians' firearm knowledge, attitudes, beliefs, and behaviors with clients. We will test these measurement tools with 100 practicing social workers recruited through professional networks, social media, and listservs. For all measures, we will address internal reliability, test-retest reliability, and construct validity, utilizing appropriate statistical procedures.

Specific Aim 2: Evaluate the preliminary efficacy of the SAFR intervention using a randomized controlled trial. An additional 100 practicing social workers (excluding participants from Aim 1) will be recruited, with  $n = 50$  allocated to each arm of the study utilizing block randomization. Participants in the control arm will receive invitations to all surveys but not to the SAFR intervention itself. We will utilize the validated measures from Aim 1 to assess changes on study variables. Results will be analyzed using either mixed linear models or generalized estimating equations as appropriate. Analyses will be performed with a focus on estimation of parameters for use in the planning of a subsequent comparative trial designed to fully assess intervention efficacy with a national sample. Supportive analyses that adjust for participant covariates will also be considered. We will also ask participants for feedback on the intervention and will track indicators of feasibility and acceptability (recruitment rates, completion of intervention and measurement tools).

*State the hypotheses to be tested, if applicable.*

*NOTE: A hypothesis is a specific, testable prediction about what you expect to happen in your study that corresponds with your above listed objectives.*

Response:

Aim 1: Our measurement tools will be reliable and valid assessments of study constructs.

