Aim 2: The SAFR intervention will improve social workers' knowledge of gun violence, attitudes about social workers' need to intervene with all clients, and behaviors regarding discussing guns and gun violence risks with clients compared to pre-test and the control group. We also hypothesize that the SAFR intervention will be feasible and acceptable.

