## Study Design\*

*Describe and explain the study design (e.g. case-control, cross-sectional, ethnographic, experimental, interventional, longitudinal, observational).*

Response:

Aim 1 is structured to provide essential tests required to establish measurement tools that are suitable to test the effectiveness of the SAFR intervention. Two surveys will be given one month apart, allowing for examination of test-retest validity.

Aim 2 is a randomized controlled trial of participation in the SAFR intervention. Participants complete pre- and posttests and a 3-month follow-up survey.

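### The Aim 2 analysis does not say how the pre-test enters the model; the likely reading is valid but usually less precise than a model with a common pre-test mean

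*Combined protocol and SAP*

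**What the plan says.** Section 19.0 (Data Management and Analysis, Aim 2) holds the quantitative plan for the trial, and Section 2.0 repeats its substance. The key sentence is "Scores on all scales will be compared over time (pre-, post-, and follow-up tests) and across groups (intervention/control groups", with linear mixed models or GEE to be used, whichever suits. The pre-test is thus one of three compared times. No mean structure and no contrast for the arm effect is given.

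The only mention of adjustment is "Supportive analyses that adjust for participant covariates will also be considered". The covariates are not named, and the pre-test score is not mentioned among them.

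The stated purpose is estimation: "Analyses will be performed with a focus on estimation of parameters for use in the planning of a subsequent comparative trial". Section 2.0 allocates 50 participants to each arm. Its hypothesis covers knowledge, attitudes and "behaviors regarding discussing guns and gun violence risks with clients compared to pre-test and the control group".

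Section 12.0 (Procedures Involved, Aim 2) fixes the order of events: "The next link will provide the pre-test assessment, including their email address for later contact. Following block randomization within REDCap", participants learn their arm.

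**The concern.** The text permits a model in which the arms share one pre-test mean, but does not call for it. Three features point to the other common form, group by time with a free pre-test mean in each arm: the pre-test is listed among the compared times, Section 2.0 speaks of assessing change, and the hypothesis is framed against both pre-test and control. With complete data, the arm effect in that model is the difference between arms in mean change.

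Because the pre-test is taken before allocation, the expected pre-test means are equal by design. A model that uses this fact discards no valid information and usually gives a narrower interval for the arm effect. That effect on each scale is one of the parameters the pilot is meant to estimate for the next trial, so its interval may be wider than the same data allow.

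The choice leaves other outputs alone. Section 2.0 says that the team "will track indicators of feasibility and acceptability (recruitment rates, completion of intervention and measurement tools"; those rates do not depend on this model, and SDs and correlations can be estimated under either one.

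**Working it through.** The plan gives no effect size, SD, power or correlation, so there is no stated figure to reproduce.

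**Inputs**
- n = 50 per arm (Section 2.0).
- Pre-test taken before randomization (Section 12.0).
- r = correlation of the pre-test with a later score: not in the documents; assumed 0.3 to 0.8.
- k = later SD divided by pre-test SD: not in the documents; k = 1 for the main table.
- Same SDs and correlation in both arms, and complete data: assumed.

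**Formulas**, in units of the later-score SD
- Separate pre-test means: Var = (2/n)(1 + 1/k² − 2r/k).
- Common pre-test mean: Var = (2/n)(1 − r²).
- Relative excess of the first over the second: (1 − rk)² / [k²(1 − r²)]. This is never negative, and is zero only when rk = 1.
- 95% CI half-width: SE times the t quantile (98 and 97 df, both about 1.98).

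**Results at k = 1**, where 2/n = 0.04 and the first variance becomes 0.04 × 2(1 − r)

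| r | Var, separate | Var, common | SE, separate v common | Half-width, separate v common | Extra participants for equal precision |
|---|---|---|---|---|---|
| 0.3 | 0.04 × 1.40 = 0.0560 | 0.04 × 0.91 = 0.0364 | 0.237 v 0.191 | 0.47 v 0.38 | 54% |
| 0.5 | 0.04 × 1.00 = 0.0400 | 0.04 × 0.75 = 0.0300 | 0.200 v 0.173 | 0.40 v 0.34 | 33% |
| 0.7 | 0.04 × 0.60 = 0.0240 | 0.04 × 0.51 = 0.0204 | 0.155 v 0.143 | 0.31 v 0.28 | 18% |
| 0.8 | 0.04 × 0.40 = 0.0160 | 0.04 × 0.36 = 0.0144 | 0.126 v 0.120 | 0.25 v 0.24 | 11% |

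The last column is the variance ratio minus 1. At r = 0.5, for example, 0.0400/0.0300 = 1.33, so the separate-means model would need about 67 per arm to match 50.

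**Sensitivity to the SD ratio** (extra participants at r = 0.3, 0.5, 0.7, 0.8)
- k = 1.25: 27%, 12%, 2%, 0%. At r = 0.8, rk = 1 and there is no gain.
- k = 0.8: 99%, 75%, 59%, 56%. Nothing in the documents supports this value; it shows direction only.

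**Cost of adjusting when it does not help.** Estimating the slope on the pre-test inflates the adjusted variance by 1 + 1/(2n − 4) = 1 + 1/96 = 1.010, or about 1%.

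**Checks**
- Simulation of 10,000 trials per setting (k = 1, one later time, change score v pre-test as covariate, true effect 0.50) gave variance ratios, adjusted over change score, of 0.65, 0.75 and 0.86 at r = 0.3, 0.5 and 0.7, against theory of 0.65, 0.75 and 0.85. Both estimators averaged 0.50, so neither is biased.
- The three-time models were compared through their information matrices, with equal correlation between all times. With complete data the SEs equal those in the table for r = 0.3, 0.5 and 0.7. With an assumed 20% lost by follow-up, half of them before the post-test, the ratios at post-test and follow-up are 0.67 and 0.70 (r = 0.3), 0.77 and 0.79 (r = 0.5), and 0.86 and 0.87 (r = 0.7). The gain shrinks slightly and keeps its direction.

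**The case against.** The strongest reply is that nothing wrong has been shown. The analysis sentence does not separate the two models: a common-mean mixed model also treats the pre-test as one of three times compared across groups. The covariates in the supportive analyses might include the pre-test, and the choice can still be made before analysis without contradicting the plan. This stands to the extent that the separate-means model is an inference. A reader might infer that the team has committed itself to an inefficient analysis; the documents do not say so. But leaving the choice open does not remove the issue. If the arms were instead compared on the later score alone, the SE would be 0.200 at any r, again valid and again less precise than the common-mean model whenever r differs from zero.

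The second reply is that the gain is small where it is most likely to be judged. Aim 1 screens the scales on one-month retest reliability, which favors higher correlations at the one-month post-test. At r = 0.7 to 0.8 and k = 1 the half-widths differ by only 0.01 to 0.03 SD. This stands for the post-test. The correlation may be lower at the three-month follow-up, where the gain would then be larger.

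Third, a reader might take the 56% to 99% excess at k = 0.8 as the size of the problem. That would need the SD to fall by a fifth in both arms, and controls receive surveys only, so no stated mechanism would shrink theirs. Those values carry no weight in the conclusion.

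Fourth, under a non-linear link, putting the pre-test in as a covariate changes the target from a marginal to a conditional effect. That is correct, and the fix allows for it.

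**Conclusion.** The point holds as one of precision and specification. The plan does not define the role of the pre-test. On the likely reading, the arm effect is a valid difference in change scores that, with equal SDs, has 11% to 54% more variance than the common-mean estimate for r between 0.8 and 0.3. The gain is close to nil where r times the SD ratio is near 1. These sizes rest on assumed correlations, SDs equal over time and between arms, and 50 per arm with complete data. The ordering itself is a large-sample result and does not depend on the particular values of r and k.

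It would go too far to infer that the planned analysis is biased or invalid. With complete data both approaches estimate the same effect without bias. Nor does the point show that the sample is too small: the plan sets no power target, and the purpose is estimation. The change is worth making because it is cheap, is justified by the design, and serves the stated purpose.

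**What to change.** In Section 19.0, Aim 2, state that for each continuous scale the main analysis is a mixed model for the three times, with time as categorical, within-person correlation modelled (structure to be stated) and one pre-test mean common to both arms. Report between-arm differences at post-test and follow-up with 95% CIs, and within-arm change from pre-test, which serves the pre-test part of the hypothesis in Section 2.0.

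The pre-test as a covariate, with a pre-test-by-time term, is an equivalent option for the arm effect when every randomized participant has a pre-test score. Within-arm change must then be reported separately, because the pre-test is no longer an outcome in that model.

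If GEE with a non-linear link is used, keep the pre-test as an outcome time with a common mean so that the effect stays marginal, or state that covariate adjustment gives a conditional effect.

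The cost is wording only: no new data or visits, and at worst about 1% in variance. The team can also gauge the likely gain at the post-test beforehand. Section 5.0 says of Aim 1: "Two surveys will be given one month apart, allowing for examination of test-retest validity". Section 13.0 places analysis of those data in April and May, before the row "Recruit for Aim 2; pre-test and course begins" starts in June. Those data would give approximate values of r and k in untreated social workers, allowing for any scales that are revised.
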